10.9. Interim Analyses

Because this is a dose-finding study, data will be reviewed on a cohort-by-cohort basis during the Phase 1a portion of the study. The purpose of these cohort-by-cohort reviews is to evaluate the safety data at each dose level and determine if a DLT has been observed. The investigators and the Lilly study team will make the determination regarding dose escalation based upon their review of the safety and tolerability data as described in this protocol.

For the Phase 1b portion of the study, 2 interim analyses are planned. The first will occur once all patients enrolled in the cohort have completed or had the opportunity to complete approximately 3 months of treatment; the second will occur once all patients enrolled in the cohort have completed or had the opportunity to complete approximately 6 months of treatment. The intent of these interim analyses is to evaluate preliminary antitumor activity. The interim analyses may also be combined with ongoing trial-level safety review or annual safety review for annual safety update reporting. No independent data monitoring committee will be required for this study.

This study will be considered complete (that is, the scientific evaluation will be complete) at a date determined by Lilly at least 60 days after the last patient has discontinued treatment with pembrolizumab and after all study objectives have been met. Study objectives may be considered as met once all enrolled patients having had opportunity for approximately 1 year follow-up from date of study enrollment. It is expected that at that time, enough data will have been obtained to assess the primary objective and the secondary objectives and allow the creation of a clinical study report. For PFS and OS, in the event that the data are not mature enough to characterize the entire survival curve, a landmark analysis at 12 months will be done for the purpose of the clinical study report. All data defined in the protocol will continue to be collected from patients who remain on treatment in the continued access period. These data may be reported separately and analyses on all patients with these data may not be performed.

11. Informed Consent, Ethical Review, and Regulatory Considerations

11.1. Informed Consent

The investigator is responsible for ensuring that the patient understands the potential risks and benefits of participating in the study, including answering any questions the patient may have throughout the study and sharing in a timely manner any new information that may be relevant to the patient's willingness to continue his or her participation in the study in a timely manner.

The ICF will be used to explain the potential risks and benefits of study participation to the patient in simple terms before the patient is entered into the study and to document that the patient is satisfied with his or her understanding of the potential risks and benefits of participating in the study and desires to participate in the study.

The investigator is ultimately responsible for ensuring that informed consent is given by each patient or legal representative before the study is started. This includes obtaining the appropriate signatures and dates on the ICF prior to the performance of any protocol procedures and prior to the administration of study drug.

11.2. Ethical Review

Lilly or its representatives must approve all ICFs before they are used at investigative sites. All ICFs must be compliant with the ICH guideline on GCP. Documentation of ERB approval of the protocol and the ICF must be provided to Lilly before the study may begin at the investigative site(s). The ERB(s) will review the protocol as required.

The study site's ERB(s) should be provided with the following:

- the current IB or package labeling (for example Patient Information Leaflet, Package Insert, or Summary of Product Characteristics) and updates during the course of the study
- ICF
- relevant curricula vitae

11.3. Regulatory Considerations

This study will be conducted in accordance with:

- 1) consensus ethics principles derived from international ethics guidelines, including the Declaration of Helsinki and Council for International Organizations of Medical Sciences (CIOMS) International Ethical Guidelines
- 2) the ICH GCP Guideline (E6)
- 3) applicable laws and regulations.

The investigator or designee will promptly submit the protocol to applicable ERB(s).

Some of the obligations of the sponsor will be assigned to a TPO.

An identification code assigned (by the investigator) to each patient will be used in lieu of the patient's name to protect the patient's identity when reporting AEs and/or other study-related data.

11.3.1. Investigator Information

Site-specific contact information may be provided in a separate document.

11.3.2. Protocol Signatures

The sponsor's responsible medical officer will approve the protocol, confirming that, to the best of his or her knowledge, the protocol accurately describes the planned design and conduct of the study.

After reading the protocol, each principal investigator will sign the protocol signature page and send a copy of the signed page to a Lilly representative.

Attachment 1. Study Schedule

I5B-MC-JGDQ(b) Baseline Assessments (Phase 1a and Phase 1b)

Relative Day Prior to Day 1 of Cycle 1	≤28	≤14	≤7	
Informed consent				
Radiological tumor assessment	X			
Medical history		X		
Demography		X		
Prior treatment therapies		X		
Physical exam		X		
Weight / BSA		X		
Vital signs		X		
ECOG performance status		X		
Concomitant medications	X			
ECG	X			
Hematology		X		
Serum chemistry		X		
Thyroid function tests		X		
Coagulation profile		X		
Urinalysis		X		
Pregnancy test			X	
Tumor measurement (palpable or visible)		X		
CTCAE v4.0 grading (Preexisting conditions)		X		

I5B-MC-JGDQ(b) Baseline Assessments (Phase 1a and Phase 1b)

Relative Day Prior to Day 1 of Cycle 1	≤28	≤14	≤7	Comments
---	-----	-----	----	----------

Abbreviations: BSA = body surface area; C1D1 = Cycle 1, Day 1; CRP = clinical research physician; CRS = clinical research scientist; CT = computed tomography; CTCAE = Common Terminology Criteria for Adverse Events; ECG = electrocardiogram; ECOG = Eastern Cooperative Oncology Group; MRI = magnetic resonance imaging; STS = soft tissue sarcoma; v = version.

I5B-MC-JGDQ(b) Treatment Period and Poststudy Assessments: Phase 1a and 1b

	Cycle 1		Cycle 2		Cycle 3-n		Follow-Up ^a		Comments
	21-day cycle		21-day cycle		21-day cycle		30-day and 90-day Safety Follow-Up ^b	Long-Term ^c	
Relative Day Within a Cycle ^d	1	8	1	8	1	8	Visit 801	Visit 802	Visit 803-8XX
Olaratumab	X	X	X	X	X	X			
Pembrolizumab	X		X		X				
Physical exam	X	X	X	X	X	X	X	X	
Weight / BSA	X		X		X				

I5B-MC-JGDQ(b) Treatment Period and Poststudy Assessments: Phase 1a and 1b

	Cycle 1		Cycle 2		Cycle 3-n		Follow-Up ^a		Comments
	21-day cycle		21-day cycle		21-day cycle		30-day and 90-day Safety Follow-Up ^b	Long-Term ^c	
Relative Day Within a Cycle ^d	1	8	1	8	1	8	Visit 801	Visit 802	Visit 803-8XX
Vital signs	X	X	X	X	X	X	X	X	
ECOG performance status	X		X		X		X	X	
ECG	X						X	X	
Hematology	X	X	X	X	X	X	X	X	

CCI

Serum chemistry	X	X	X	X	X	X	X	X	CCI
-----------------	---	---	---	---	---	---	---	---	-----

I5B-MC-JGDQ(b) Treatment Period and Poststudy Assessments: Phase 1a and 1b

	Cycle 1		Cycle 2		Cycle 3-n		Follow-Up ^a		Comments
	21-day cycle		21-day cycle		21-day cycle		30-day and 90-day Safety Follow-Up ^b	Long-Term ^c	
Relative Day Within a Cycle ^d	1	8	1	8	1	8	Visit 801	Visit 802	Visit 803-8XX
Thyroid function tests	X				X		X	X	
Coagulation profile	X				X				
Urinalysis	X				X				
Pregnancy test	X		X		X		X	X	
CTCAE v4.0 grading	X		X		X		X	X	X
Concomitant meds	X		X		X		X	X	

CCI

PK sampling	See Attachment 4 for specific time points			CCI			
-------------	---	---	---	---	--	--	-----

I5B-MC-JGDQ(b) Treatment Period and Poststudy Assessments: Phase 1a and 1b

	Cycle 1		Cycle 2		Cycle 3-n		Follow-Up ^a		Comments
	21-day cycle		21-day cycle		21-day cycle		30-day and 90-day Safety Follow-Up ^b	Long-Term ^c	
Relative Day Within a Cycle ^d	1	8	1	8	1	8	Visit 801	Visit 802	Visit 803-8XX

CCI

Immunogenicity	See Attachment 4 for specific time points	See Attachment 4 for specific time points		See Attachment 4 for specific time points					CCI
Pharmacogenetics whole blood sample	X								
Tumor measurements (palpable or visible)			X		X			X	

I5B-MC-JGDQ(b) Treatment Period and Poststudy Assessments: Phase 1a and 1b

	Cycle 1		Cycle 2		Cycle 3-n		Follow-Up ^a			Comments
	21-day cycle		21-day cycle		21-day cycle		30-day and 90-day Safety Follow-Up ^b		Long-Term ^c	
Relative Day Within a Cycle ^d	1	8	1	8	1	8	Visit 801	Visit 802	Visit 803-8XX	
Radiological tumor assessment					X		X	X	X	CCI
Collection of survival information							X	X	X	
Collection of post-study-treatment anticancer therapy information							X	X	X	

Abbreviations: AE = adverse event; BP = blood pressure; BSA = body surface area; C = cycle; CRF/eCRF = case report form/electronic case report form; CT = computed tomography; CTCAE = Common Terminology Criteria for Adverse Events; D = day; ECG = electrocardiogram; ECOG = Eastern Cooperative Oncology Group; hrs = hours; IRR = infusion-related reaction; irRECIST = immune-related Response Evaluation Criteria In Solid Tumors; MRI = magnetic resonance imaging; olara = olaratumab; PD = progressive disease; pembro = pembrolizumab; PK = pharmacokinetic; RR= respiration rate; SAEs = serious adverse events.

I5B-MC-JGDQ(b) Treatment Period and Poststudy Assessments: Phase 1a and 1b

- ^a No follow-up procedures will be performed for patients who withdraw informed consent unless he or she has explicitly provided permission and consent.
- ^b **30-day and 90-day Safety follow-up** begins the day after the patient and the investigator agree that the patient will no longer continue study treatment and lasts approximately 90 days (± 7 days). The date of this agreement is to be reported on the CRF as the date of discontinuation from study treatment. Visit 801 should occur approximately 30 days (± 7 days) after the decision to discontinue treatment. Visit 802 begins 1 day after the 30-day safety follow-up period ends and lasts approximately 60 days. If it is deemed to be in the best interest of the patient to start a new anti-cancer treatment prior to the scheduled end of the follow-up visits, the visit duration may be shortened. In this case, the follow-up assessments should be completed prior to the initiation of the new therapy.
- ^c **Long-term follow-up (Visits 803-8XX)** begins the day after 90-day safety follow-up is completed.
Follow-up for progression: Patients that discontinue study treatment for reasons other than progression will be followed every 6 weeks (± 7 days) until PD or initiation of other anticancer therapy. Additional radiologic assessments are permissible at the discretion of the investigator.
Follow-up for survival: All patients will be followed every 2 months (± 7 days) for the first 2 years, then every 6 months (± 14 days) until the patient's death or overall study completion.
- ^d A window of ± 3 days will be permitted due to holidays, weekends, inclement weather or other unforeseen circumstances, including unexpected changes in patient schedules, and will not count as a protocol deviation. In later cycles, longer delays may be allowed in consultation with Lilly medical representative.

I5B-MC-JGDQ(b) Continued Access Period

	Continued Access Period ^a		Comments
	Visit 501 - 5XX	Follow-Up Visit 901 ^b	
	21-day cycle		
Relative Day within a Cycle^c	1	8	
Olaratumab	X	X	
Dosing information	X		
PK sampling / Immunogenicity			
CTCAE v4.0 grading	X	X	

CCI

Abbreviations: AE = adverse event; CTCAE = Common Terminology Criteria for Adverse Events; eCRF = electronic case report form; IRR = infusion-related reaction; PK = pharmacokinetics; SAE = serious adverse event.

^a The continued access period (Visits 501-5XX) begins after study completion and ends at the end of trial (see Section 6.2.1). Following study completion, patients without disease progression who continue to experience clinical benefit and no undue risks may continue to receive study treatment until disease progression, death, unacceptable toxicity, or start of new anticancer treatment. During this period, investigators may perform standard procedures and tests not shown here as needed to treat and evaluate patients; however, Lilly will not routinely collect the results of these assessments.

^b The continued access follow-up visit (Visit 901) begins 1 day after the patient and the investigator agree that the patient will no longer continue treatment in the continued access period and lasts approximately 30 days (± 7 days). If it is deemed to be in the best interest of the patient to start a new anti-cancer treatment prior to the scheduled end of the follow-up visit, the visit duration may be shortened. In this case, the follow-up assessments should be completed prior to the initiation of the new therapy.

^c Delays of up 7 days will be permitted due to holidays, weekends, inclement weather or other unforeseen circumstances and will not count as a protocol deviation.

Attachment 2. Clinical Laboratory Tests

Clinical Laboratory Tests

Hematology^a

Hemoglobin
Hematocrit
Erythrocyte count (RBC)
Leukocytes (WBC)
Neutrophils
Lymphocytes
Monocytes
Eosinophils
Basophils
Platelets

Coagulation^b

aPTT
PT/INR

Urinalysis^b

Specific gravity
pH
Protein
Glucose
Ketones
Blood
Urine leukocyte esterase
pH

Clinical Chemistry^a

Sodium
Magnesium
Potassium
Total bilirubin
Alkaline phosphatase
Alanine aminotransferase (ALT/SGPT)
Aspartate aminotransferase (AST/SGOT)
Blood urea nitrogen
Creatinine
Uric acid
Calcium
Glucose, random
Albumin
Total protein
Chloride
Bicarbonate
Direct bilirubin
Creatinine clearance
Phosphorus
Lipase

Thyroid Function Tests^a

T3 (or FT3)
FT4
Thyroid Stimulating Hormone (TSH)

Serum or Urine Pregnancy Test (females only)^b

Abbreviations: aPTT = activated partial thromboplastin time; FT3 = free triiodothyronine; FT4 = free thyroxine; PT/INR = international normalized ratio of prothrombin time; RBC = red blood cells; SGOT = serum glutamic oxaloacetic transaminase; SGPT = serum glutamic pyruvic transaminase; T3 = triiodothyronine; WBC = white blood cells.

a Assayed by Lilly-designated central laboratory.

b Local or investigator-designated laboratory.

Attachment 3. Hepatic Monitoring Tests for Treatment Emergent Abnormality

Selected tests may be obtained in the event of a treatment emergent hepatic abnormality and may be required in follow up with patients in consultation with the Lilly clinical research physician.

Hepatic Monitoring Tests

Hepatic Hematology^a	Haptoglobin^a
Hemoglobin	
Hematocrit	Hepatic Coagulation^a
RBC	Prothrombin Time
WBC	Prothrombin Time, INR
Neutrophils, segmented	
Lymphocytes	Hepatic Serologies^{a,b}
Monocytes	Hepatitis A antibody, total
Eosinophils	Hepatitis A antibody, IgM
Basophils	Hepatitis B surface antigen
Platelets	Hepatitis B surface antibody
	Hepatitis B Core antibody
Hepatic Chemistry^a	Hepatitis C antibody
Total bilirubin	Hepatitis E antibody, IgG
Direct bilirubin	Hepatitis E antibody, IgM
Alkaline phosphatase	
ALT	Anti-nuclear antibody^a
AST	
GGT	Anti-smooth muscle antibody^a
CPK	

Abbreviations: ALT = alanine aminotransferase; AST = aspartate aminotransferase; CPK = creatine phosphokinase; GGT = gamma glutamyl transferase; Ig = immunoglobulin; INR = International Normalised Ratio; RBC = red blood cells; WBC = white blood cells.

^a Assayed by Lilly-designated or local laboratory.

^b Reflex/confirmation dependent on regulatory requirements and/or testing availability.

**Attachment 4. Pharmacokinetic, Biomarker,
Pharmacogenetics, and Immunogenicity Sampling
Schedules**

CCI

CCI

CCI

Attachment 5. Recommendations for Reporting Serious Adverse Events

Recommendations for Reporting Serious Adverse Events

When contacting Lilly to report a SAE, please have the following information available:

Patient Demographics

- patient identification (number), sex, date of birth, origin, height, and weight

Study Identification

- full trial protocol number, investigator's name, investigator's number

Study Drug

- drug code or drug name, unit dose, total daily dose, frequency, route, start dose, cycle details, start date and last dose date (if applicable)

Adverse Event

- description, date of onset, severity, treatment (including hospitalization), action taken with respect to study drug, clinical significance, test and procedure results (if applicable)

Relationship to Study Drug & Protocol Procedures

Concomitant Drug Therapy

- indication, total daily dose, duration of treatment, start date, action taken

In Case of Death

- cause, autopsy finding (if available), date, relationship to study drug and protocol procedures.

Attachment 6. ECOG Performance Status

Eastern Cooperative Oncology Group (ECOG) Performance Status

Activity Status	Description
0	Fully active, able to carry on all pre-disease performance without restriction
1	Restricted in physically strenuous activity but ambulatory and able to carry out performance of a light or sedentary nature, for example, light housework, office work
2	Ambulatory and capable of all selfcare but unable to carry out any work activities. Up and about more than 50% of waking hours
3	Capable of only limited selfcare, confined to bed or chair more than 50% of waking hours
4	Completely disabled. Cannot carry on any selfcare. Totally confined to bed or chair
5	Dead

Source: Oken et al. 1982.

Attachment 7. Creatinine Clearance Formula

Note: This formula is to be used for calculating CrCl from **local laboratory results only**.

*For serum creatinine
concentration in mg/dL:*

$$\text{CrCl} = \frac{(140 - \text{age}^a) \times (\text{wt}) \times 0.85 \text{ (if female), or } \times 1.0 \text{ (if male)}}{72 \times \text{serum creatinine (mg/dL)}}$$

For serum creatinine concentration in $\mu\text{mol/L}$:

$$\text{CrCl} = \frac{(140 - \text{age}^a) \times (\text{wt}) \times 0.85 \text{ (if female), or } \times 1.0 \text{ (if male)}}{0.81 \times \text{serum creatinine} \text{ } (\mu\text{mol/L})}$$

^a age in years, weight (wt) in kilograms.

Reference: Cockcroft and Gault 1976.

-OR-

$$\begin{aligned} \text{GFR}(\text{mL/min}/1.73\text{m}^2) &= 170 \times [\text{PCr}]^{0.999} \times [\text{age}]^{-0.176} \\ &\times [0.762 \text{ if patient is female}] \times [1.18 \text{ if patient is black}] \\ &\times [\text{SUN}]^{-0.17} \times [\text{Alb}]^{+0.318} \end{aligned}$$

PCr= Plasma Creatinine, mg/dL; SUN= Serum urea nitrogen, mg/dL; Alb= Serum albumin, g/dL
Source: Murray and Ratain 2003

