6.1. Study Population

6.1.1. Inclusion Criteria

Patients may be included in the study if they meet all of the following criteria during screening prior to the first dose of study drug.

- [1] Have histologically confirmed diagnosis of unresectable locally advanced or metastatic STS, not amenable to curative treatment and after available standard therapies (per local guidelines) have failed to provide clinical benefit, or been deemed inappropriate candidates for additional standard treatments by the investigator.

Patients with a diagnosis of Grade 1 liposarcoma (atypical lipomatous neoplasms) are eligible if there is histological or radiographic evidence of evolution to more aggressive disease.

- [2] Is ≥ 18 years of age.
- [3] Are willing and able to perform written informed consent for the trial and are amenable to compliance with protocol schedules and testing.
- [4] Have measurable or nonmeasurable but evaluable disease as defined by Response Evaluation Criteria in Solid Tumors (RECIST version 1.1 [v1.1]; Eisenhauer et al. 2009).

[5] Have adequate organ function, as defined in the table below, with all screening labs performed within 14 days of first dose of study treatment.

System	Laboratory Value
Hematological	
Absolute neutrophil count (ANC)	$\geq 1.5 \times 10^9/L$
Platelets	$\geq 100 \times 10^9/L$ (platelet transfusions are not allowed within 2 weeks prior to Study Day 1, see Exclusion Criterion [20])
Hemoglobin	$\geq 9 \text{ g/dL}$ or $\geq 5.6 \text{ mmol/L}$ (packed red blood cell transfusions are not allowed within 2 weeks prior to Study Day 1, see Exclusion Criterion [20])
Renal	
Creatinine or Measured or calculated ^a creatinine clearance (CrCl) (GFR may be used in place of creatinine or CrCl) (Attachment 7)	$\leq 1.5 \times \text{ULN}$ or $\geq 60 \text{ mL/min}$
Hepatic	
Total bilirubin	$\leq 1.5 \times \text{ULN}$
AST (SGOT) and ALT (SGPT)	$\leq 2.5 \times \text{ULN}$ or $\leq 5 \times \text{ULN}$ for patients with liver metastases
Coagulation	

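### As supplied, the GFR equation in Attachment 7 rises with plasma creatinine and contradicts the CrCl formula beside it; the sign needs checking on the original page

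*Protocol*

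**What the plan says.** Protocol Section 6.1.1, criterion 5, sets the renal limits as "\leq 1.5 \times \text{ULN}$ or $\geq 60 \text{ mL/min": the first for creatinine, the second for measured or calculated CrCl. It adds "GFR may be used in place of creatinine or CrCl) (Attachment 7". A GFR value used this way is naturally read against the limit of 60.

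Attachment 7 then offers two calculations as alternatives.

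- **CrCl.** Creatinine is in the denominator, "72 \times \text{serum creatinine (mg/dL", with a second version for creatinine in µmol/L.
- **GFR.** The equation starts "170 \times [\text{PCr}]^{0.999} \times [\text{age}]^{-0.176", has sex and race factors, and ends with "SUN}]^{-0.17} \times [\text{Alb}]^{+0.318". The units are "PCr= Plasma Creatinine, mg/dL; SUN= Serum urea nitrogen, mg/dL; Alb= Serum albumin, g/dL".

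A footnote to criterion 5 leaves the calculation of CrCl to institutional practice. It does not mention GFR, so the equation in Attachment 7 is the only GFR method that the protocol supplies.

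**The concern.** The two formulas serve one entry limit, so they should rank patients in the same order. As printed they rank them in opposite orders: higher creatinine lowers CrCl and raises GFR. The other three exponents in the GFR equation carry explicit signs (−0.176, −0.17, +0.318); only the one on creatinine has none.

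At stake is whether an entry rule works as written. The renal limits are joined by an or, and GFR may replace either measure. A patient who fails on creatinine and on CrCl could therefore meet the letter of the criterion through the GFR equation.

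**Working it through.** The plan gives no worked GFR value, so there is no figure of its own to reproduce.

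**Formulas (Attachment 7)**

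- GFR = 170 × PCr^e × age^−0.176 × sex factor × race factor × SUN^−0.17 × Alb^0.318, with e = +0.999 as printed. The alternative e = −0.999 is an assumption, used only for comparison.
- CrCl = (140 − age) × weight × sex factor / (72 × creatinine).

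**Assumed patient (not from the documents):** man, age 60, not black, albumin 4.0 g/dL, 70 kg, with urea nitrogen (SUN) rising with creatinine. Both factors are then 1.

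**Step 1. Are the two CrCl versions consistent?** Taking 88.4 µmol/L per mg/dL as the unit conversion, 72/88.4 = 0.814, which matches the 0.81 in the µmol/L version. The CrCl pair agrees with itself, so the conflict lies with the GFR equation.

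**Step 2. One case in full: creatinine 3.0, SUN 40.**

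- The terms are 60^−0.176 = 0.486, 40^−0.17 = 0.534 and 4.0^0.318 = 1.554. Their product with 170 is about 68.6.
- As printed: 68.6 × 3.0^0.999 = 68.6 × 2.997 ≈ 206.
- Exponent reversed: 68.6 / 2.997 ≈ 23.
- CrCl: 80 × 70 / (72 × 3.0) = 5600/216 ≈ 26.

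**Step 3. Other values of creatinine.**

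| Creatinine (mg/dL) | SUN (mg/dL) | GFR as printed | GFR, exponent reversed | CrCl |
|---|---|---|---|---|
| 1.0 | 15 | 81 | 81 | 78 |
| 2.0 | 28 | 146 | 36 | 39 |
| 3.0 | 40 | 206 | 23 | 26 |
| 5.0 | 60 | 320 | 13 | 16 |

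At creatinine 1.0 the sign makes no difference. Above it, the printed equation and CrCl diverge. With the sign reversed they agree closely.

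**Step 4. Does this depend on the assumed patient?** The GFR equation was evaluated over ages 18 to 90, SUN 20 to 150, albumin 2.0 to 4.5, both sexes and both race factors.

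- Creatinine 3.0: 94 to 350 as printed; 10 to 39 reversed.
- Creatinine 5.0: 156 to 584 as printed; 6 to 23 reversed.
- Creatinine 2.0: the printed minimum is 94 × (2/3)^0.999 ≈ 62.

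The printed value exceeds 60 in every combination. Rising SUN does not cancel the effect: if SUN rises in proportion to creatinine, the net exponent is still 0.999 − 0.17 = +0.829.

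**Step 5. Would the other two routes flag the Step 2 patient?** Creatinine 3.0 exceeds 1.5 × ULN for any ULN below 3.0/1.5 = 2.0 mg/dL. CrCl would reach 60 only at a weight of 60 × 72 × 3.0 / 80 = 162 kg. Under the assumptions made, only the GFR equation as printed lets this patient through.

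The GFR equation is indexed to 1.73 m² and the limit is in mL/min. No adjustment was made for this; it does not affect the direction of the error.

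**The case against.** **The sign may have been lost in reading the PDF.** The equation reached this text by machine, and a superscript minus is easily dropped. Two other minus signs survived, which argues against a general loss. But the equation also prints a plus on its one explicitly positive exponent, so a bare 0.999 looks like a missing character, and the text cannot show who dropped it. This objection stands, and it makes the point conditional.

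**Other controls would catch the patient.** A reader might infer that patients in renal failure would be enrolled. The documents do not support that as the expected outcome. The GFR route is optional. Creatinine and CrCl are both in the central chemistry panel (Attachment 2), and serum chemistry is scheduled at baseline (Attachment 1). Site and sponsor must confirm eligibility before enrolment (Section 7.3). Exclusion criterion 17 covers serious conditions and laboratory abnormalities at the investigator's judgement. A value near 206 at creatinine 3.0 would also look odd. These controls reduce the chance of wrongful enrolment, but they do not correct the equation. Section 6 permits no waivers of entry criteria, so the written rule should be right.

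**A healthy patient might seem to be shut out.** At creatinine 0.6 and SUN 12 the printed equation gives 51 for the assumed man. This has no effect on entry: he qualifies on creatinine for any ULN of 0.4 mg/dL or more (0.6/1.5).

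**Adverse event grading and DLT attribution might seem to be at risk.** This is not shown. Preexisting conditions are graded at baseline (Attachment 1), SAP Section 6.13.2 counts an event as treatment-emergent only if it is new or has worsened, and Section 7.2.2.2 excludes toxicity clearly due to another cause from the DLT definition.

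**Conclusion.** The contradiction is real in the supplied text: the two alternative formulas in Attachment 7 move in opposite directions as creatinine rises. At creatinine 2.0 mg/dL or more, the printed GFR exceeds the entry limit in every combination tried. In the worked case it is about 206, against 26 by CrCl.

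The size rests on assumed patient values. The direction follows from the printed sign, and the range in Step 4 does not overturn it. That the intended exponent is −0.999 is inferred from the agreement with CrCl in Step 3; the documents do not state it.

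This is a low-severity correction, conditional on the original page. No endpoint, estimate, sample size or escalation rule uses the equation.

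**What to change.** 1. Look at the GFR equation on the original protocol page. If the minus is there, nothing needs correcting and the point falls away.
2. If it is absent, check the exponent against the source that Attachment 7 cites and correct it, or delete the GFR alternative there and in criterion 5. Either way, the remaining text should give one consistent direction.
3. In that case, identify any patient who qualified on GFR and recheck the renal criterion from the recorded creatinine and CrCl.

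The cost is one character or one deletion, issued as a protocol correction, plus a look at the screening records of at most about 37 planned patients. Sample size, visit schedule and analysis are unaffected.
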